4.5 Methods

4.5.1 Schedule of assessments

At least one baseline assessment is required for all study participants where both a blood draw of 60ccs (for the use of platelet function testing, biospecimen collection), non-invasive vascular function imaging testing and endothelial vein harvesting will occur (table 1). A subject can choose not to participate in any baseline testing they feel uncomfortable with but must participate in one baseline assessment to be included in the study.

4.5.2 Longitudinal component (Group 1 only)

After baseline assessment, those with moderate to severe psoriatic disease will be offered by the study physician randomly the opportunity for longitudinal follow up and to take either aspirin and/or atorvastatin. For 2 weeks +/- 4 days, 1/4th of the subjects enrolled will be offered 81mg of aspirin, 1/4th of the subjects enrolled will be offered atorvastatin 40mg, ¼ will be offered both aspirin and atorvastatin and 1/4th will be offered nothing. Participants will be given the opportunity to only participate in the baseline assessment and opt out of the opportunity to take aspirin and/or atorvastatin and longitudinal component.

Both aspirin and atorvastatin are routinely used and approved in medical practice for the primary prevention of coronary artery disease. These medications are frequently used in the psoriatic population based on national guidelines when a calculated cardiac risk score is elevated (considered at moderate to high risk of cardiovascular events). These medications will be obtained from the Tisch outpatient pharmacy. They will be stored and dispensed with CTSI oversight. A drug accountability and storage log will be kept as per NYU research protocol.

A follow up assessment will be planed (table 1) at 2 weeks +/- 4 days and will include repeat blood draw (60 ccs, for the use of platelet function testing, biospecimen collection) and repeated endothelial vein harvesting. The end of the study is considered when the subject completes the follow up assessment. All study drugs will be stopped at this time. If the subject wishes to continue the study drugs they will be referred to their primary medical provider for further management.

A subject will be able to opt out of any part of the follow up assessment they desire. If a subject agrees to be started on aspirin and/or atorvastatin for the longitudinal part of the analysis and therapy for psoriasis is planned by the referring provider, we will attempt to perform the longitudinal follow up prior to their starting medication. Participation in this study will not impact planned treatment of the subjects by their primary provider.

All subjects may be asked to provide additional information about their medical history, update any interim history and provide additional samples as noted above. Health information will be monitored overtime by review of the medical chart. Additional questions may be asked by phone or during routine clinical follow-up, as appropriate.

Table 1. Patient Group		Baseline	Longitudinal Analysis	Follow-up
1 n = 40	Moderate to severe psoriatic disease	1) Blood 2) Endothelial vein harvesting 3) Vascular function imaging	Offered: 1) Aspirin 2) Atorvastatin	1) Blood 2) Endothelial vein harvesting 3) Additional medical history

				obtained
2 n = 10	Healthy Controls	1) Blood 2) Endothelial vein sampling 3) Vascular function imaging		1) Additional medical history obtained

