4.2 Inclusion/Exclusion Criteria for Psoriatic Patients

Inclusion Criteria

1. Group 1: Subjects with a history of moderate to severe psoriatic disease
2. Age ≥ 18 & < 90
3. Able and willing to provide written informed consent for the study

Exclusion Criteria

1. Unable to speak Spanish or English
2. Active smoking (within the past year)
3. Autoimmune, rheumatologic or inflammatory disease which are not psoriasis or psoriatic arthritis
4. Known active cancer receiving treatment
5. Pregnancy
6. Anemia (hemoglobin < 9 mg/dl) or thrombocytopenia (Platelet count < 75), or thrombocytosis (Platelet count > 600)
7. A history of severe bleeding or bleeding disorders
8. Current medication use which interact with either aspirin or atorvastatin
9. Chronic kidney disease (CrCl < 30 ml/min)
10. Congestive heart failure
11. Currently taking aspirin or a statin.
12. NSAID use within the past 48 hours

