We will evaluate the association between moderate to severe psoriatic disease and measures of thrombotic risk. As in Aim1, linear and nonlinear regression models will be employed to investigate the difference in platelet activity between those with and without psoriasis. This is gauged by monocyte platelet activity (MPA) and assessing monocyte – platelet interaction after adjusting for other covariates and applying model selection procedures. We will collect data including maximal aggregation (%), slope of the aggregation curve, and elapsed time between addition of agonist and onset of aggregation (lag phase). Regression models will unveil how these characteristics are influenced by those exposed to psoriatic disease, adjusting for other covariates.

c. Aim 3

We will then investigate how traditional medications used in CVD prevention such as aspirin and statins affect vascular function and thrombotic risk in those with moderate to severe psoriatic disease. We will assess baseline endothelial vein transcriptome data, genetic expression for routine markers of endothelial activation such as VCAM-1, ICAM-1, NF-kB and platelet reactivity data. Using paired t- tests, we will assess the changes to platelet reactivity and endothelial function with the use of aspirin, aspirin plus atorvastatin or atorvastatin therapy.

11. Safety and Adverse Events

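### Patients with psoriasis therapy planned can enter the 2-week drug phase with only a best-effort promise to sample first, so a change due to that therapy may be counted as a study-drug effect in Aim 3

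*Combined protocol and SAP*

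**What the plan says.** Section 4.5.2 (Longitudinal component) covers the case directly. The condition is "If a subject agrees to be started on aspirin and/or atorvastatin for the longitudinal part of the analysis and therapy for psoriasis is planned" (the provider who refers the patient does the planning). The response is that "we will attempt to perform the longitudinal follow up prior to their starting medication". It continues: "Participation in this study will not impact planned treatment of the subjects by their primary provider". The follow-up timing is "A follow up assessment will be planed (table 1) at 2 weeks +/- 4 days", that is, day 10 to day 18. The drug offer is random in quarters: aspirin, atorvastatin, and then "¼ will be offered both aspirin and atorvastatin and 1/4th will be offered nothing".

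In section 4.2 the exclusion nearest to the point is "Current medication use which interact with either aspirin or atorvastatin". The other medication criteria concern aspirin, statins and recent NSAIDs. None concerns new, changed or stable psoriasis therapy.

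Some data capture exists. Section 4.4 has staff review medication use at the baseline interview. Table 1 lists additional medical history at follow-up, and the text above it allows interim history and chart review. No start date is required, and no use in the analysis is stated.

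For Aim 3, section 10c states: "Using paired t- tests, we will assess the changes to platelet reactivity and endothelial function with the use of aspirin", atorvastatin or the two together. It names no covariates, no rule for patients who start psoriasis therapy, and no comparison with the quarter offered no drug.

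**The concern.** The sentence on attempting an early follow-up shows that the authors saw the risk: therapy begun between the two samples could itself move the markers. Section 2 refers to studies of psoriasis treatment and endothelial dysfunction, so the protocol treats this outcome domain as one that such therapy may affect. Recruitment includes patients approached after visits to dermatology and rheumatology clinics, so some may have therapy planned, although the documents do not say how many.

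A within-arm pre/post test attributes all change between the two samples to the study drug. It cannot separate a drug effect from the effect of anything else begun in the interval. With about 10 patients per arm, a few starters could move an arm mean noticeably. Section 9 says the trends are meant to support further study proposals, so a misattributed change could carry forward.

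**Working it through.** **The plan's own figure.** Section 9 gives 74% power for the longitudinal part with n = 10 per group, d = 0.8 and alpha 0.05. For a paired t-test the noncentrality is d·√n = 0.8 × √10 = 2.53 on 9 degrees of freedom.

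- One-sided (critical value 1.833): 75.4%, within 2 points of the stated figure.
- Two-sided (critical value 2.262): 61.6%.
- Two-sample comparison, 10 v 10: 53.0% one-sided, 39.5% two-sided.

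The 74% therefore fits a one-sided within-arm pre/post test, although section 9 words it as a difference between groups. This agrees with section 10c: the planned inference is within-arm. The sidedness is not stated; two-sided 0.05 is used below.

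**Bias from starters.** Let m of 10 patients in an arm start psoriasis therapy before the follow-up sample, and let it shift the marker by s, in SDs of the pre/post change. With no study-drug effect the expected arm mean change is (m/10) × s. For example, 1 starter at 0.4 gives 0.04 SD, 3 at 0.8 gives 0.24 SD, and 4 at 1.5 gives 0.60 SD.

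**Chance of a significant improvement.** Simulated one-sample t-test on 10 changes (SD 1), two-sided 0.05, at least 200,000 runs per setting, counting only results in the improving direction:

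| Starters of 10 | s = 0.4 | s = 0.8 | s = 1.5 |
|---|---|---|---|
| 0 | 2.5% | 2.5% | 2.5% |
| 1 | 3% | 4% | 4% |
| 2 | 4% | 5.5% | 8% |
| 3 | 5% | 8% | 13% |
| 4 | 6% | 12% | 22% |

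The inputs m and s are assumptions, as is the improving direction. For scale, s = 0.8 equals the drug effect that section 9 assumes, and s = 1.5 is nearly twice that.

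**Is the within-arm test the cause?** If a drug arm and an untreated arm of 10 each have the same number of starters (0 to 5, s = 0.8), a two-sided test of the difference in change rejects in 5.0% down to 3.4% of runs. So the inflation comes from the pre/post test. This protection needs similar starting rates in both arms, and the best-effort sentence in section 4.5.2 covers only patients who agree to study drug.

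**Cost of leaving starters out.** Paired-test power at d = 0.8:

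| n | One-sided | Two-sided |
|---|---|---|
| 10 | 75.4% | 61.6% |
| 9 | 70.7% | 55.9% |
| 8 | 65.3% | 49.6% |
| 7 | 59.0% | 42.8% |

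**The case against.** The strongest reply is that this is a small pilot, that the authors already intend to sample before new therapy starts, and that medication and interim-history review are in place. Recruitment also runs through general medicine clinics, fliers, earlier study participants, social media and the patient portal. Because baseline is a separate appointment, therapy planned at a clinic visit might begin before the first sample and not between the two. The documents give no starting rate and no two-week effect of psoriasis therapy. With 1 or 2 starters and a modest shift the inflation is slight. All of this stands, and it limits what can be said about size. It does not close the gap, because none of it says how a patient is handled when the attempt fails.

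A reader might go further and infer that a patient who starts therapy on, say, day 5 will be sampled at days 10–18 and kept in the paired test. The documents do not say so; the handling is unspecified. A reader might also infer that psoriasis therapy would lower NF-kB, the adhesion molecules and platelet activation, and so flatter the study drugs. Section 2 gives no direction, does not tie its remark on psoriasis treatment to these markers or to platelets, and says nothing about onset within two weeks. The text supports may affect, and no more.

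Making an analysis without the starters the main estimate is also tempting. That would be an exclusion after allocation, which can itself be informative, and with 7 of 10 left it would cut two-sided power from 62% to 43%. It belongs in a sensitivity analysis.

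**Conclusion.** The point holds as a design and analysis gap: entry is open to patients with therapy planned, sampling first is best effort only, handling after a failed attempt is unstated, and the planned test cannot separate the two sources of change. Under the plan as written, an effect of new psoriasis therapy may be counted as an aspirin or atorvastatin effect.

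How much this matters is unknown. The calculation runs from near-negligible (about 3–6% against 2.5%, with 1–2 starters at 0.4–0.8 SD) to material (about 8–22%, with 3–4 starters at 0.8–1.5 SD). It assumes 10 analysed patients per arm, no true drug effect, a shift in the hoped-for direction and a two-sided test. The case for changing the plan rests on the low cost of the remedy, and on the difficulty of repairing the problem later without recorded dates, more than on any one of these percentages.

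**What to change.** 1. Section 4.5.2: at the existing baseline medication review, and before the random offer, ask about planned new or changed psoriasis therapy. Keep patients whose planned start falls before the earliest follow-up day (14 − 4 = day 10) in the baseline part only. State that no one's treatment is delayed or altered for the study.
2. Follow-up visit: record the start date and type of any psoriasis therapy begun since baseline, using the medical history already collected there. Do this in all four quarters.
3. Section 10c: keep all followed patients in the main Aim 3 estimate. Prespecify a sensitivity analysis without samples taken after new psoriasis therapy began. Compare change in the drug arms with change in the quarter offered no drug, where that quarter has follow-up samples.
4. Reconcile section 4.4, which ties follow-up assessments to patients who agree to aspirin or atorvastatin, with section 4.5.2 and Table 1, so that it is clear whether the undrugged quarter is sampled again.

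The cost is one baseline question, a date and a type field, and a few sentences of analysis text. The downside is somewhat fewer patients in the longitudinal part and lower precision in the sensitivity analysis: n = 7 instead of 10 lowers two-sided power at d = 0.8 from 62% to 43%.

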4.5.3 Vascular function assessment

Vascular function may be assessed either using brachial artery flow mediated dilatation (FMD) or pulse wave velocity (PWV), both non-invasive ultrasound measures of vascular function. FMD and PWV will be measured using a duplex ultrasound imaging system (2D, grayscale B-mode imaging, pulsed Doppler and color flow Doppler) with a 11 MHz linear array probe (Sonosite Inc., Bothell WA). Collection of the ultrasound vascular function data will occur in the Clinical Research Center of the NYU Clinical and Translational Science Institute (CTSI), under the direction of [name], who is on this proposal.

Before each study, participants will provide answers to a brief series of questions to determine eligibility for the FMD/PWV measurements and to determine which arm to use. Participants will rest supine for at least 20 minutes before measurements are made. We will attempt to use the right arm for imaging except in a few uncommon circumstances among patients eligible for this study (recent injury with or without casting on the right arm, right mastectomy with lymph node removal, or any other condition that results in immobility, pain, and/or swelling in the right arm or hand). The participants will be positioned to maximize their comfort and to facilitate image acquisition by the sonographer. A standard 3-lead electrocardiogram will be placed on the torso (right upper torso, left upper torso, and left lower torso) as per protocol. Resting supine blood pressure will be measured in the left arm and recorded.

Mean blood flow velocity (MBFV, cm/sec) will be determined by calculation of the area under the hand-traced curve of the spectral display. Brachial artery diameter and MBFV will be measured at rest, and after transient arterial occlusion induced by inflation of a forearm blood pressure cuff to suprasystolic pressure for 5 minutes. MBFV will be measured for 15 seconds immediately upon release of the occluding cuff; the first 5 beats after release will be averaged. Occlusion of brachial artery blood flow for 5 minutes with suprasystolic pressures may result in mild hand numbness and discomfort that resolves quickly with decompression of the blood pressure cuff without any known clinical sequelae. Brachial artery diameter will be measured over a 1 cm vessel length at end-diastole 60-75 seconds following release of the occluding cuff; 3 diameter measurements will be averaged. FMD will be calculated as the % change in brachial artery diameter after cuff release compared with the resting diameter. Internal and external landmarks will be used to make repeated measurements at the same vessel site. In our laboratory, mean FMD in normal adult subjects mean age 43 years is 5.89% (95% CI 4.53%, 7.23%). Intraobserver coefficient of variance for FMD measurements of the same vessel is 1-2%. Within-subjects coefficient of variance ranges from 5-10% for same day measurements (reliability coefficient for repeated measures 72%) and 15-30% for day-to-day measurements (reliability coefficient for repeated measures 46%). Carotid-to-femoral arterial pulse wave velocity as well as central arterial

pressure (Sphygmacor), a surrogate measure of vascular stiffness associated with long-term risk of cardiovascular event will also be recorded.

4.5.4 Endothelial cell harvesting

There will be a maximum of two time points for endothelial cell harvesting and biospecimen collection. Endothelial harvesting will take place either in the CTSI or in the NYU Seligman Center for Advanced Therapeutics. Both of these centers have access to nursing support and ancillary support staff including trained phlebotomists. All subjects will have their blood drawn and endothelial harvesting after informed consent and completion of the screening interview. If willing to the subjects will be preferably fasting > 4 hours and water intake is allowed. They will be in a reclined position with feet elevated. An angiocatheter ≤ 21 gauge will be inserted into a peripheral vein on the upper extremity using aseptic technique. A 0.021in. diameter J-shaped wire (Daig, Minnetonka, MN) or a 0.018in. diameter J-shaped wire (Arrow, Reading, PA) will be then advanced into the angiocatheter, to a distance of 4cm beyond the end of the angiocatheter. Angiocatheters and J shaped wire described above are routinely used for intravenous fluids and medication administration in this hospital. Venous endothelial cells will be scraped from the intimas of superficial forearm veins by repeated (3 times) insertion and removal of the wire. The distal portion of the wire will be transferred to a 50ml conical tube containing dissociation buffer (0.5% bovine serum albumin, 2 mM EDTA, and 100 microg/ml heparin in PBS, pH 7.4) and maintained at 4°C until study. Half of retrieved endothelial cells will be used for RNA extraction and a half for immunofluorescence.

The angiocatheter used will be a ≤ 21 gauge (typically 20 gauge) INSYTE autoguard IV catheter which is routinely used for clinical care, IV hydration and administration of medications. In this case we will using this angiocathter off label as a method to safety access the peripheral vein. This poses a non-significant risk for the device according to 21 CFR 812.3 (m) because: 1) There is NO implantation of the device. 2) This device will not be used to sustain human life and does not pose a serious risk to health or safety of the subject. 3) This device will not be used to diagnose, cure, mitigate or treat a disease. 4) This angiocatheter device is routinely used across the country in clinics and hospitals and does not pose a serious risk to health, safety or welfare of the subject.

The J – wire used will be either a 0.021in. diameter J-shaped wire (Daig, Minnetonka, MN) or a 0.018in. diameter J-shaped wire (Arrow, Reading, PA). This device will be used off label as a means of accessing and collected endothelial cells. In clinical practice these devices are typically used in hospital settings as a guidewire for accessing human veins and threading other catheters into the vein. These wires therefore routinely come into contact of vein walls during clinical care. HOWEVER, our use is to harvest endothelial cells that come into contact with these wires. Therefore, this is considered off label. This poses a non-significant risk for the device according to 21 CFR 812.3 (m) because: 1) There is NO implantation of the device. 2) This device will not be used to sustain human life and does not pose a serious risk to health or safety of the subject. 3) This device will not be used to diagnose, cure, mitigate

or treat a disease. 4) This j-wire device is routinely used across the country in clinics and hospitals and does not pose a serious risk to health, safety or welfare of the subject.

4.5.5 Biospecimen collection

Study blood will be collected by trained staff in the outpatient clinics, Seligman Center for Advanced Therapeutics or in the CTSI. This will occur immediately after endothelial vein harvesting using the same brachial IV site if the subject has agreed to endothelial vein harvesting. If the subject declined endothelial vein harvesting but agrees to a blood draw, then standard techniques of blood drawing will be used as follows. After cleansing of the venipuncture site with an alcohol wipe and removal of excess alcohol with sterile gauze, a tourniquet will be applied to the patient's bicep region. A 20G butterfly needle or less will be inserted into the antecubital vein, the tourniquet will be removed, and free-flowing blood will be collected with minimal trauma and stasis. The needle will be removed when blood collection is complete and sufficient pressure will be applied using sterile gauze at the puncture site until cessation of bleeding. A sterile band-aid will be applied to cover the venipuncture site. .

For each patient, no more than 60 ml (≈4 tablespoons and 1/8 of a standard blood donation) of blood will be collected at the baseline visit in red (no anticoagulant) top, lavender (EDTA anticoagulant) top, green (heparin) and blue (sodium citrate anticoagulant) top tubes). We believe this amount of blood is negligible and presents minimal risk for the patient. Approximately 30 cc of blood will be used for the different measurements of platelet function, lipid levels, coagulation, inflammation, and approximately 30 cc of blood will be used for isolation of RNA, microRNA and storage of DNA at -80C. . The samples will be stored in the PI's lab at the NYU Science building 7th floor without any identifying information other than a code number. These samples will be barcoded system and lab vantage and stored in a freezer with back-up power supply.

4.5.6 Longitudinal Follow Up Data Collection

Participants enrolled in the longitudinal part of this study will be offered the option to participate in follow-up biospecimen collection. This follow-up will allow us to assess how aspirin and/or atorvastatin affect platelet and endothelial function and inflammation. This follow-up component will consist of additional blood samples of ≈ 30ml (2 tablespoons or less) that will be collected for different measurements of platelet function, lipid levels, coagulation, inflammation, and approximately 30 ccs of blood will be used for isolation of RNA, microRNA and storage of DNA at -80C. The samples will be stored in the PI's lab at the NYU Science building 7th floor without any identifying information other than a code number. Repeat endothelial vein harvesting will also be performed as described above.

Overall, code numbers used for collection of samples will not be based on any information that could be used to identify the subject (for example, social security number, initials or birth date). The master list linking names to code numbers will be kept in a locked file cabinet, separate from all research information.

If participating in the optional follow-up collection, the total amount of blood withdrawn (baseline plus follow up) will be no more than 120 ml (approximately 7 tablespoons and 1/4 for a standard blood donation). This amount of blood collection is within established safety guidelines of research blood collection in adults. Blood collection at baseline and at the follow up time points will allow us to examine how the treatment of aspirin and atorvastatin modify 1) endothelial vein function in psoriatic disease, 2) changes to platelet activity and 3) alterations in coagulation and inflammation in those with psoriatic disease.

For all cases and controls, we will call 1 week after each procedure to assess how patients are feeling after endothelial vein harvesting. Adverse events will be managed as mentioned below.

